8.1.2. Planned Secondary Efficacy Statistical Analyses

8.1.2.1. Number of critical errors made after 1st Healthcare Professional (HCP) instructions

Secondary Statistical Analyses
Endpoint(s)
The percentage of subjects making at least one critical error after the: 
 • first instruction from the HCP
Model Specification, Model Checking & Diagnostics, Model Results Presentation

 • Same method as percentage of subjects making at least one critical error after reading the PIL(s), see Section 7.1.2 • Note this model will only be fitted if there is sufficient data. If there is insufficient data then only summary statistics will be produced.

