9.1.1. Assessment of Errors in Use of Device

Within each sub-study, subjects will be randomised for the order of treatment. One treatment will require subjects to demonstrate use of a single inhaler (ELLIPTA), while the other treatment will require the subject to demonstrate use of 2 inhalers (DISKUS-HandiHaler in Sub Study 1 or Turbuhaler-HandiHaler in Sub Study 2).

Subjects will be provided with the relevant section of the PIL, explaining correct use, for each inhaler they are to be tested on. The critical and over all errors per inhaler and how these have been defined are included in Appendix 2.

The errors listed will be in aligned with the correct use information from the respective PILs, in a checklist for each inhaler and these will be provided to HCPs for scoring errors during the study conduct. The checklists will be provided in the Study Reference Manual.

Figure 2 depicts the process flow for assessing inhaler use errors and further details are provided, for each treatment, in Section 9.1.1.1 and Section 9.1.1.2.

Figure 2 Assessment of errors in use for each DPI tested**9.1.1.1. Assessment of ELLIPTA error in use**

Subject will be asked to read the patient instruction leaflet for ELLIPTA and then demonstrate ELLIPTA use. Any errors (critical or non-critical) made by the subject while using the ELLIPTA will be recorded by the HCP on the checklist provided. If the subject makes no errors, this will also be recorded by the HCP, and there will be no further assessments. If the subject makes any error in the use of the ELLIPTA, the HCP will provide instruction in the correct use of the ELLIPTA to the subject. The subject will then demonstrate ELLIPTA use again. If the subject makes no errors, this will be recorded by the HCP and there will be no further assessments. If the subject again makes errors in the use of the ELLIPTA any errors will be recorded by the HCP. The HCP will again provide instruction in the correct use for the final time, following which the subject will then demonstrate ELLIPTA use one final time. Any errors made during this demonstration will be recorded. There will be no further assessments. In total, the HCP can provide instruction in the use of the inhaler up to two times.

9.1.1.2. Assessment of DISKUS-HandiHaler in Sub Study 1, or Turbuhaler-HandiHaler in Sub Study 2, for error in use

Subjects will be provided with 2 inhalers and 2 PILs dependent on which sub study they are included in.

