Subjects should be tested on each DPI provided consecutively, they will be tested in the following order for each sub study.

- Sub Study 1: DISKUS followed by HandiHaler

- Sub Study 2: Turbuhaler followed by HandiHaler

Subjects will be asked to read the patient instruction leaflet for the first DPI (DISKUS or Turbuhaler) and then demonstrate first DPI use. Any errors (critical or non-critical) made by the subject while using the first DPI will be recorded by the HCP on the checklists provided. If the subject makes no errors, this will also be recorded by the HCP and there will be no further assessment for this first DPI. If the subject makes any error in the use of the first DPI, the HCP will provide instruction in the correct use of the inhaler to the subject. The subject will then demonstrate inhaler use again. If the subject makes no errors, this will also be recorded by the HCP and there will be no further assessments for this DPI. If the subject again makes errors in the use of the DPI, the HCP will record the errors and provide instruction in correct use for the final time. The subject will then demonstrate use of first DPI for one final time. Any errors or correct use after this demonstration will be recorded, and there will be no further assessments for this DPI. In total, the HCP can provide instruction in the use of the first DPI up to two times.

This assessment will then be repeated with HandiHaler.

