8.1.2.2. Number of overall errors made

Secondary Statistical Analyses
Endpoint(s)

 • Percentage of subjects making at least one overall error after reading the PIL(s) • Percentage of subjects making at least one overall error after the first instruction from the HCP
Model Specification, Model Checking & Diagnostics, Model Results Presentation

 • Same method as percentage of subjects making at least one critical error after reading the PIL(s), see Section 7.1.2 • Sensitivity analysis will also be performed as detailed in Section 7.1.2 • Note this model will only be fitted if there is sufficient data. If there is insufficient data then only summary statistics will be produced.

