11.5.3. Critical and Overall Errors

Critical and Overall errors

An ordinal variable (error) will be derived to indicate where a participant had any error, or any critical error whilst demonstrating correct device use. If the subject has an overall/critical error the error=Y whilst if they did not have an overall/critical error then error=N. The variables errty/errtycd will be used to determine whether the variable error is referring to a critical or overall error.

An ordinal variable (err_ord) will be derived to indicate the responses of critical error based on comparing responses for the device sequences used. This variable will be used in the sensitivity analysis for critical error data.

If the sequence of inhaler use is ELLIPTA in the 1st period and DISKUS + HandiHaler or Turbuhaler + HandiHaler in the 2nd period, then for critical error in relation to sequence:
 
 err_ord = -1, if subject had critical error in the 1st period but NOT in the 2nd period err_ord = 1, if subject had critical error in the 2nd period but NOT in the 1st period err_ord = 0, if subject had critical errors in BOTH periods or had NO critical errors in BOTH periods

If the sequence of inhaler use is and DISKUS + HandiHaler or Turbuhaler + HandiHaler in the 1st period and ELLIPTA in the 2nd period, then for each preference question:
 
 err_ord = 1, if subject had critical error in the 1st period but NOT in the 2nd period err_ord = -1, if subject had critical error in the 2nd period but NOT in the 1st period err_ord = 0, if subject had critical errors in BOTH periods or had NO critical errors in BOTH periods

The above method also applies to overall errors.

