11.5.5. Number of instructions

Number of Instructions

The number of instructions from the HCP which are needed to demonstrate adequate inhalation technique for each inhaler will be summarised. The number of instruction from the HCP will be assigned as follows:

- NUMINSTR = 0, if no instruction needed correct after reading leaflet
- NUMINSTR = 1, if the participant received 1st instruction and had no error
- NUMINSTR = 2, if the participant received the 2nd instruction and had no error
- NUMINSTR = 3, if the participant received 2nd instruction and had at least one error

From this an ordinal variable (diffinst) will be derived to indicate the difference between the number of instructions required to demonstrate correct use on the ELLIPTA device compared to the DISKUS + HandiHaler or Turbuhaler + HandiHaler devices.

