11.12. Appendix 12: Example Mock Shells for Data Displays

Example : EFF_T01
Protocol : 206215
Population : Intent to Treat

Page 1 of 1

Table X.X
Summary of errors on ELLIPTA

Sub-study 1: ELLIPTA vs DISKUS + HandiHaler

Inhaler errors test	After Reading Leaflet (N=XXX)	After 1st Instruction from HCP (N=XXX)	After 2nd Instruction from HCP (N=XXX)
Number of Subjects with Errors	XXX (XX%)	XXX (XX%)	XXX (XX%)
Number of Subjects with Critical Errors	XXX (XX%)	XXX (XX%)	XXX (XX%)
Total Number of Errors	XXX	XXX	XXX
Total Number of Critical Errors	XXX	XXX	XXX
Failed to open cover [1]	XXX (XX%)	XXX (XX%)	XXX (XX%)
Shook the device upside down after dose preparation [1]	XXX (XX%)	XXX (XX%)	XXX (XX%)
Inhalation manoeuvre: long, steady, deep	XXX (XX%)	XXX (XX%)	XXX (XX%)
Blocked air inlet during inhalation manoeuvre	XXX (XX%)	XXX (XX%)	XXX (XX%)
No exhalation before an inhalation	XXX (XX%)	XXX (XX%)	XXX (XX%)
Exhaled directly into mouthpiece [1]	XXX (XX%)	XXX (XX%)	XXX (XX%)
No seal by the lips round the mouthpiece during the inhalation [1]	XXX (XX%)	XXX (XX%)	XXX (XX%)
Did not hold breath	XXX (XX%)	XXX (XX%)	XXX (XX%)
Did not close the device	XXX (XX%)	XXX (XX%)	XXX (XX%)

[1] Indicates a Critical Error.

Note: Percentages for number of subjects are calculated from the total number of subjects who used the device(s), percentage of type of errors are calculated based on the number of subjects with errors.

Programming notes: Percentages for rows 1 and 2 are calculate from the total number of subjects in the ITT population shown in the heading, the remaining percentages are calculated based on the total number of subjects who had errors. Page by sub-study. For DISKUS + HandiHaler/Turbuhaler + HandiHaler the first page should only contain the first four rows which will the overall summary of number of subjects with errors/critical errors and total number of errors/critical errors. The remaining two pages will be a replicate of the shell above but for two devices separately.

Example : EFF_T02
Protocol : 206215
Population : Intent to Treat

Table X.X
Summary and Analysis of Time (Minutes) Taken to Demonstrate Correct Inhaler Use

Sub-study 1: ELLIPTA vs DISKUS + HandiHaler
Assessment: Time to read the PIL and Demonstrate Correct Use

	ELLIPTA (N=XXX)	DISKUS + HandiHaler (N=XXX)
n	XXX	XXX
Mean	XX.XX	XX.XX
SD	XX.XXX	XX.XXX
Median	XX.XX	XX.XX
Min	XX.X	XX.X
Max	XX.X	XX.X
Number of Subjects who demonstrated correct use	XXX	XXX

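### After HCP instruction, does the paired error model lose every subject who was already correct on one option?

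*SAP*

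**What the plan says.** - **Model.** SAP 8.1.2.1, on critical errors after the first instruction: "Same method as percentage of subjects making at least one critical error after reading the PIL(s), see Section 7.1.2". SAP 8.1.2.2 applies the same method to "Percentage of subjects making at least one overall error after the first instruction from the HCP", and SAP 9.1.1.1 to both endpoints after the second instruction. All three fall back to summary statistics if the data are too sparse to fit the model.
- **Data collection.** Protocol 9.1.1.1, on ELLIPTA after the leaflet: "If the subject makes no errors, this will also be recorded by the HCP, and there will be no further assessments". Protocol 9.1.1.2, on the first inhaler of the combination: "there will be no further assessment for this first DPI". The same procedure is then followed for HandiHaler. Any error, critical or not, triggers instruction.
- **Outcome.** SAP 11.5.3: "An ordinal variable (error) will be derived to indicate where a participant had any error, or any critical error whilst demonstrating correct device use". The value is Y if there was an error and N if there was not.
- **Parallel endpoints.** SAP 11.5.5: "NUMINSTR = 0, if no instruction needed correct after reading leaflet". SAP 8.1.2.4 likewise sets T2 to zero for a subject who was correct after the leaflet.
- **Denominators in shell EFF_T01 (SAP 11.12).** The programming note reads "Percentages for rows 1 and 2 are calculate from the total number of subjects in the ITT population shown in the heading". The table note reads "Percentages for number of subjects are calculated from the total number of subjects who used the device(s").

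**The concern.** A conditional logistic model stratified by subject learns only from subjects with an outcome on both options, and among those only from discordant pairs. After instruction, an inhaler that was right first time has no demonstration. If the model ran only on demonstrations that took place, a subject correct at once on ELLIPTA but still failing on the combination would drop out, although that subject is direct evidence of a difference. What remained would be a subset chosen by outcome.

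There is a second hazard. SAP 11.6.2.2 counts a missing checklist response as an error. If a step that was never due were treated as missing, early success would be scored as failure.

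Two secondary endpoints (critical and overall errors after the first instruction) and two endpoints classed as other (after the second) are exposed in each sub-study.

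**Working it through.** **The plan's own figure.** The only power figure is for the primary, leaflet-stage comparison: at least 90% with 72 subjects (Protocol 10.2). With 10,000 simulated trials per row of the rate table, independence within subject and a likelihood-ratio test with period in the model, power is 96.1% to 97.1%, consistent with that lower bound. It depends on the test: a Wald test with period, counting separated samples as non-significant, gives 59% to 81%. The plan gives no figure for the post-instruction endpoints.

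**What each reading would give.** The documents state neither overall-error rates nor post-instruction rates, so the rates here are assumptions. Let qE and qC be the probabilities of any error after the leaflet on ELLIPTA and on the combination. Let rE and rC be the probabilities of the relevant error after the first instruction among those instructed. Assume independence. The odds ratio (OR) is ELLIPTA against combination.

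- Recorded pairs only: subjects = 72·qE·qC; OR = rE(1−rC) / [rC(1−rE)].
- Already correct = N: a = qE·rE, b = qC·rC; OR = a(1−b) / [b(1−a)]; all 72 subjects are used.
- Already correct = Y: a′ = a + 1 − qE, b′ = b + 1 − qC; OR = a′(1−b′) / [b′(1−a′)].

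*Case 1: q = 40%/70%, r = 10%/20%.*
- Recorded pairs: 72 × 0.4 × 0.7 = 20.2 subjects. Discordant: 20.2 × (0.1×0.8 + 0.2×0.9) = 5.2. OR = 0.08/0.18 = 0.44.
- N: a = 0.04, b = 0.14. Discordant: 72 × (0.04×0.86 + 0.14×0.96) = 12.2. OR = 0.0344/0.1344 = 0.26.
- Y: a′ = 0.64, b′ = 0.44. OR = (0.64×0.56)/(0.44×0.36) = 2.26.

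*Case 2: q = 35%/60%, r = 20%/10%.*
- Recorded pairs: 72 × 0.35 × 0.6 = 15.1 subjects. OR = 0.18/0.08 = 2.25.
- N: a = 0.07, b = 0.06. OR = (0.07×0.94)/(0.06×0.93) = 1.18.

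So the reading matters numerically, but the recorded-pairs odds ratio is not always nearer 1. In case 1 it is nearer 1; in case 2 it is farther away. Allowing a latent within-subject correlation of 0.3 at 35%/60% gives the same pattern: 0.39 against 0.23 with 10%/20%, and 2.60 against 1.19 with 20%/10%.

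**Which reading the plan supports.**
1. *The derivation.* SAP 11.5.3 has two branches. A subject who needed no instruction on an inhaler had no error on it after instruction, and so falls in the N branch.
2. *Who is included.* SAP 11.6.2 excludes subjects who complete only one period. Those who complete both devices but skip the questionnaire stay in every analysis except preference. Dropping a two-period completer for being correct too early would breach that rule. SAP 8.1.1 also bases the secondary analyses on ITT.
3. *The missing-data rule.* SAP 11.6.2 defines missing data as data that were requested and not supplied. A demonstration that the protocol says shall not take place was not requested, so the Y reading does not fit.
4. *The shells.* EFF_T06 classifies subjects on both options against one total N and is repeated at the later timepoints. The EFF_T01 programming note uses the ITT number, and that shell includes the post-instruction columns.
5. *The parallel endpoints.* Zero instructions and T2 = 0 already carry early success forward as success.
6. *The combination.* The EFF_T05 footnote counts failure on either inhaler as failure of the option. Applied to errors, an inhaler already used correctly adds none, and the other inhaler decides.

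**The EFF_T01 notes.** The table note refers to use of the device, not to a demonstration at that step. The two denominators therefore differ only for ITT subjects who never used that option, and Protocol 10.2 expects no withdrawals.

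**The case for a change.** The strongest case for a change is that the authors wrote the carry-forward rule for the number of instructions and for T2, but not for the error endpoints. Table shells are not model rules, and 11.5.3 speaks of errors made while demonstrating use. The trial is open-label, so an unwritten choice could in principle be made with results in view. The condition that data must suffice does not close the gap, because whether they suffice depends on how the outcome is defined. The cost would be a sentence or two.

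What stands is that the sentence is absent and that the readings give different odds ratios. What does not stand is that the readings are equally open. Recorded pairs only conflicts with 11.6.2 and the ITT basis, and scoring the step as an error conflicts with the definition of missing data. Nor does the planned code run on raw demonstrations: SAP 7.1.2 applies it to a variable derived under 11.5.3. Whether early-correct inhalers have rows at later steps depends on the eCRF and dataset specification, which are not among the documents. The added sentence would record the convention already implied; it would not alter the analysis.

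**Conclusion.** No change to the plan is needed. The gap is one of detail, and analysts following the rest of the SAP would fill it sensibly: an inhaler already used correctly counts as error-free at later steps, the combination counts as in error if either inhaler still is, and all two-period completers stay in.

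Under the assumed rates the less supported readings would matter (0.44 or 2.26 instead of 0.26 in case 1; 2.25 instead of 1.18 in case 2). Both the size and the direction rest on rates that the documents do not give. The exposure is limited to two secondary and two other endpoints per sub-study, with models fitted only where data allow. The primary endpoint and its sample size are unaffected, since every subject who completes both periods is assessed on both options after the leaflet.

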8.1.2.2. Number of overall errors made

Secondary Statistical Analyses
Endpoint(s)

 • Percentage of subjects making at least one overall error after reading the PIL(s) • Percentage of subjects making at least one overall error after the first instruction from the HCP
Model Specification, Model Checking & Diagnostics, Model Results Presentation

 • Same method as percentage of subjects making at least one critical error after reading the PIL(s), see Section 7.1.2 • Sensitivity analysis will also be performed as detailed in Section 7.1.2 • Note this model will only be fitted if there is sufficient data. If there is insufficient data then only summary statistics will be produced.

8.1.2.3. Number of instructions (maximum of 2) from the HCP

Secondary Statistical Analyses
Endpoint(s)

 • Number of instructions from the HCP

Secondary Statistical Analyses
Model Specification

 The endpoint of number of instructions from the HCP will be analysed using the Intent-to-treat population. Those who were unable to demonstrate correct use will not be included in the analysis, but will be summarised in tables This endpoint will be analysed using the Wilcoxon signed rank test
Model Results Presentation

 Summary statistics on the number of instructions from the HCP will be provided for each device along with the p-value of the Wilcoxon signed rank test.
SAS Code

The following SAS code will be used:
 <pre>proc univariate data=no_error; var diffinst; run;</pre> 
diffinst is derived as shown in Section 11.5.5

8.1.2.4. Training/Teaching time required

Secondary Statistical Analyses
Endpoint(s)

 Total demonstration time (T1+T2)
Model Specification

 The endpoint of training/teaching time will be analysed using the Intent-to-treat population. This endpoint will be analysed using Kaplan-Meier analysis.
Model Results Presentation

 For DISKUS + HandiHaler or Turbuhaler + HandiHaler the time for each device will be added together to form the total time needed to demonstrate correct use at T1 and T2 respectively. Median time to correctly use the inhaler after reading the patient information leaflet and HCP's instruction (T1+T2) will be presented for each inhaler group. For subjects who correctly used the inhaler after reading the patient information leaflet set T2=0. T1+T2 is censored for subjects who did not use the inhaler correctly after 3 attempts. Kaplan-Meier survivor functions of T1+T2 will be obtained for each inhaler group and plotted on the same figure. In the above analysis the median time will be taken from the Kaplan Meier model.
SAS Code

 Kaplan-Meier survivor functions of the proportion of subjects with a time to correctly use the inhaler will be obtained for each inhaler group separately and will be plotted on the same figure. The following SAS code will be used: <pre>ods output ProductLimitEstimates = plest(keep = trtcd timeto failed left) quartiles=median CensoredSummary=cen; proc lifetest data=t_device outsurv=survest; time timeto*event(0); strata treatment; run;</pre>

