To compare the Training/Teaching Time required to demonstrate correct inhaler use	
 • The total amount of time taken to demonstrate correct inhaler use (T1+T2). • The amount of time taken to read the patient information leaflet and demonstrate correct inhaler use (T1) ^d • The amount of time taken to be given instruction by the HCP (up to 2 times) on use of the inhaler and to demonstrate correct inhaler use (T2) ^d
Preference attributes for each treatment option tested ^b	Treatment preference, from questionnaire for: 
 • Number of steps required to take COPD medication • Over all treatment preference
a. Over all and critical errors for each inhaler tested, as well as an explanation of how these endpoints were defined, are listed in Appendix 2 b. Preference Questionnaires for each sub-study are included in Appendix 3 c. To show correct inhaler use a subject demonstrates the use of the inhaler without making any critical or non-critical error d. Endpoint will be treated as 'other endpoint' and not secondary for the statistical analysis	

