5.4. Scientific Rationale for Study Design

This design has been used in previous studies looking at critical errors and/or preference of inhalers in patients with COPD and naive to the inhalers tested. The cross-over design was chosen to allow the subjects to serve as their own control in their ability to use both the ELLIPTA DPI and the other combination DPIs. A single visit is suitable for assessing these endpoints and reduces inconvenience of multiple visits for subject included.

Placebo inhalers are used to remove any bias due to treatment effect, avoid the need for wash-in/-out periods, and to avoid the need to withhold or discontinue current COPD medications, which may affect the subject's clinical status (improvement or decline) and perceptions, as noted above.

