7.2. Method of Treatment Assignment

All participants will be centrally randomized using an Interactive Web Response System (IWRS). Before the study is initiated, the log in information & directions for the IWRS will be provided to each site.

Participants will be assigned in equal numbers to one of four sequences for the sub-study they are included on, in accordance with the randomization schedule generated by Clinical Statistics, prior to the start of the study and using validated internal software.

The possible sequences for each sub study are shown in Table 1 and Table 2

Table 1 Sub Study 1 Treatment Sequences

Sequence	Period 1	Period 2	Preference Questionnaire
A	ELLIPTA	DISKUS + HandiHaler	1
B	DISKUS + HandiHaler	ELLIPTA	2
C	ELLIPTA	DISKUS + HandiHaler	2
D	DISKUS + HandiHaler	ELLIPTA	1

Table 2 Sub Study 2 Treatment Sequence

Sequence	Period 1	Period 2	Preference Questionnaire
E	ELLIPTA	Turbuhaler + HandiHaler	3
F	Turbuhaler + HandiHaler	ELLIPTA	4
G	ELLIPTA	Turbuhaler + HandiHaler	4
H	Turbuhaler + HandiHaler	ELLIPTA	3

Study treatments will be dispensed at the study visit summarized in SOA

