10.4. Statistical Analyses

10.4.1. Efficacy Analyses

Endpoint	Statistical Analysis Methods
Primary	
The primary endpoint is the percentage of subjects making at least one critical error after reading the PIL(s).
 
This endpoint will be analysed using conditional logistic regression with subject as fixed strata, and treatment option and period as fixed effects. The odds ratio, 95% CI and p-value will be presented for the comparison between treatment options. It will be based on a two-sided hypothesis testing approach of superiority.

Secondary	
The following endpoints will be analysed in the same way as for the primary endpoint if there are sufficient subjects making errors otherwise the data will be summarised only:
 
 The percentage of subjects making at least one critical error after the first instruction from the HCP The percentage of subjects making at least one overall error after reading the PIL(s) The percentage of subjects making at least one overall error after the first instruction from the HCP 
The number of instructions (0, 1 or 2 times) from the HCP which are needed to demonstrate correct inhaler use will be analysed using the Wilcoxon signed rank test.
 
The total amount of time taken to demonstrate correct inhaler use (T1+T2)

Endpoint	Statistical Analysis Methods
	
will be analysed using Kaplan-Meier methods.
 
Treatment preference from questionnaire will be analysed using a Cochran-Mantel-Haenszel test, adjusted for study inhaler use sequence.

Other	
Analysis of the following other endpoints will be defined in the Reporting and Analysis Plan.
 
 • The percentage of subjects making at least one critical error after the second instruction from the HCP • The percentage of subjects making at least one overall error after the second instruction from the HCP • The amount of time taken to read the patient information leaflet and demonstrate correct inhaler device use (T1) • The amount of time taken to be given instruction by the HCP on use of the inhaler and demonstrate correct inhaler use (T2)

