Secondary Analyses	
 The number of critical errors made by COPD patients after instruction from the Healthcare Professional (HCP) for each treatment option tested will be analysed using conditional logistic regression with subject as fixed strata, and treatment option and period as fixed effects. The number of overall (critical and non-critical) errors made by COPD patients, after a subject has read the PIL(S) or after Instruction from the HCP for each treatment option tested, will be analysed using conditional logistic regression with subject as fixed strata, and treatment option and period as fixed effects. The number of instructions (maximum of 2) from a HCP which is needed to demonstrate correct inhaler use will be analysed using Wilcoxon sum rank test. The Training/Teaching Time required to demonstrate correct inhaler use will be analysed using Kaplan-Meier plots and summary statistics. Preference attributes for each treatment option tested will be analysed using the Cochran-Mantel-Haenszel test.

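### Total training time (T1+T2) gets a valid descriptive Kaplan-Meier display but no within-subject estimate, confidence interval or p-value, although the objective is comparative and SAP Table 4 marks a formal analysis

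*SAP*

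**What the plan says.** Protocol section 4 lists the secondary objective "To compare the Training/Teaching Time required to demonstrate correct inhaler use". Its footnote d moves T1 and T2 taken singly to other endpoints, so T1+T2 remains secondary. Protocol 10.4.1 says T1+T2 "will be analysed using Kaplan-Meier methods" and names no contrast or test. The SAP synopsis says training time "will be analysed using Kaplan-Meier plots and summary statistics".

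SAP 8.1.2.4 says "This endpoint will be analysed using Kaplan-Meier analysis". The curves are "obtained for each inhaler group separately and will be plotted on the same figure", a median is taken from each, and subjects who still make errors after three attempts are censored. The code is PROC LIFETEST with "strata treatment" and no subject, period or sequence term. Its ODS statement keeps product-limit estimates, quartiles and censoring counts.

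SAP Table 4 ticks the Stats Analysis column for T1+T2, and the table's notes define that column as formal analysis such as modelling. Shell EFF_T02, whose title promises both a summary and an analysis, gives for each option n, mean, SD, median, range, counts of correct and failed use, and the Kaplan-Meier median. It has no row for a difference, interval or p-value. On the design, Protocol 5.4 says "The cross-over design was chosen to allow the subjects to serve as their own control".

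**The concern.** Every subject who completes the visit provides a time on both options, so the within-subject difference is available and is what the crossover was chosen to deliver. The plan leaves it unused. The report could put two medians side by side but could not say how large the difference is, how precisely it is known, or whether inhaler order affected it.

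The Table 4 tick adds a practical risk. Someone programming a formal analysis from this text has only the LIFETEST code to work from. The test it yields by default is an unpaired log-rank test, which is the wrong one for two records from the same person.

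**Working it through.** **1. The plan's own figure.** Neither document gives a power, effect size, SD or correlation for training time. The 72 subjects per sub-study and the power of at least 90% in Protocol 10.2 concern critical errors only. There is nothing to reproduce for this endpoint, and the inputs in steps 4 to 6 are assumptions apart from the 72 subjects.

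**2. The secondary endpoints side by side.**

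| Endpoint | Method in SAP 8.1.2 | Within-subject information | Shell reports |
|---|---|---|---|
| Errors | Conditional logistic regression, subject as stratum, period in model | Used | Odds ratio, CI, p (EFF_T04) |
| Instructions | Wilcoxon signed rank on the difference | Used | Median difference with CI, p (EFF_T05) |
| Preference | Cochran-Mantel-Haenszel by inhaler order | Each answer is itself a comparison | p (EFF_T03) |
| T1+T2 | Kaplan-Meier per option | Not used | Per-option summaries only (EFF_T02) |

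Training time is the only one without an inferential result. No paired or order-adjusted analysis of time appears elsewhere in either document.

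**3. What the code could supply.** With a STRATA statement, LIFETEST prints a log-rank test by default. It would treat 2 × 72 = 144 times as coming from 144 independent people. The ODS statement does not keep it and EFF_T02 has no place for it.

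**4. Precision on the log scale.** With n subjects, common SD σ and within-subject correlation ρ, the variance of the difference in means is 2σ²(1−ρ)/n. An unpaired analysis assumes 2σ²/n. The ratio of true to assumed standard error is √(1−ρ): √0.7 = 0.84 at ρ = 0.3, √0.5 = 0.71 at 0.5, and √0.3 = 0.55 at 0.7. The unpaired test therefore overstates its own error, which makes it conservative.

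**5. Simulation.** 5,000 runs of 72 subjects on two options; log-normal times, log SD 0.6; median ratio exp(0.2) = 1.22; 10% censoring per option unrelated to time; no period effect; two-sided 5%. The unpaired log-rank test is set against a paired test on log-rank scores, so that only the pairing changes.

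| ρ | Size, unpaired | Size, paired | Power, unpaired | Power, paired |
|---|---|---|---|---|
| 0 | 4.5% | 4.2% | 40% | 39% |
| 0.3 | 2.8% | 5.4% | 41% | 49% |
| 0.5 | 1.2% | 4.3% | 39% | 59% |
| 0.7 | 0.3% | 4.8% | 36% | 74% |

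The simulation standard error for a power near 40% is √(0.4 × 0.6/5,000) = 0.7 percentage points, so the gaps from ρ = 0.3 upwards are not noise.

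**6. Dependence on the effect size.** A second setting used log SD 0.5, no censoring and 2,000 runs, with unpaired log-rank against signed rank. For ELLIPTA times 15% shorter, power was 44% v 62% (ρ = 0.3), 41% v 76% (0.5) and 41% v 94% (0.7). For 25% shorter it was 92% v 98%, 94% v 99.6% and 98% v 100%. At 40% shorter both tests reached 100%. In the 15% case at ρ = 0 the figures were 41% v 47%, so part of this gap comes from the change of test and not from pairing. Step 5 is the fairer measure.

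**7. Cost of adjusting for order.** On allocation, Protocol 7.2 says "Participants will be assigned in equal numbers to one of four sequences". Two of the four sequences start with ELLIPTA, so 72 subjects split into 36 and 36. Let D be the period 1 minus period 2 time, with variance v, period effect π and treatment effect τ. D has mean π+τ in one order and π−τ in the other. Half the difference between the two order means estimates τ free of π, with variance ¼(v/36 + v/36) = v/72. That equals the variance of a simple mean of 72 within-subject differences, so in large samples the adjustment costs nothing.

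**The case against.** The strongest defence is that the time analysis is descriptive by intent. The protocol names no test, the synopsis speaks of plots and summary statistics, the code keeps no test output, and EFF_T02 has no p-value row. On that reading the figures in step 5 describe a test that nobody plans to report. This stands: those figures show what would follow if the code were used for inference, and are not properties of a planned result. It does not explain the comparative objective or the Table 4 tick.

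Several stronger readings are tempting, and the documents do not support them.

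- A reader might infer that the objective goes unanswered or that no valid comparison is made. Each curve uses one record per subject, so pairing does not invalidate it. The full summaries, the success and failure counts and the overlaid curves are a fair descriptive comparison.
- A reader might infer a risk of false positives. With positive correlation the error runs the other way: the unpaired test rejects too rarely.
- A reader might infer a large loss of power in this trial. The comparator time adds two leaflets and two devices against one, so a large difference is plausible, and step 6 shows little loss in that case.
- A reader might infer a firm contradiction with SAP 11.8.1, which says inhaler sequence is used throughout. That section opens by listing covariates that may be used, and EFF_T05 openly states that its own analysis ignores sequence. With equal allocation, a common period shift affects both options about equally.

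**Conclusion.** The point holds as a gap in inference on one secondary endpoint. The objective and Table 4 call for a comparison, while SAP 8.1.2.4 and EFF_T02 deliver separate descriptions and leave pairing and order unused. The primary analysis conditions on subject and is unaffected.

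The size depends on quantities that the documents do not give. Under the step 5 assumptions, pairing adds about 8 percentage points of power at correlation 0.3 (49 − 41), 20 at 0.5 (59 − 39) and 38 at 0.7 (74 − 36). It adds nothing at correlation 0. Positive correlation is plausible when the same person reads the leaflets and handles the inhalers at one visit, but its value is unknown. The simulated censoring was unrelated to time; in the trial, those who fail three times are probably the slower subjects. The simulated paired test is also not identical to the rank test proposed below, so the figures indicate direction and rough size. The case for the change rests less on power than on obtaining an effect estimate with an interval from data already collected.

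**What to change.** In SAP 8.1.2.4, pre-specify the within-subject difference in T1+T2 (ELLIPTA minus comparator) as the comparison, tested by a rank test of period differences between the two inhaler orders.

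State the failure rule with it. Failure on one option only is ranked as the most extreme difference against that option. Failure on both is a tie, with difference zero. As EFF_T05 already does for the number of instructions, failure on either comparator device should count as failure on that option.

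Report the median (Hodges-Lehmann) difference with its 95% CI where these are finite, and say so where they are not. The shift between orders in period differences is twice the treatment difference, so it must be halved. Add estimate, CI and p-value to EFF_T02, and keep the Kaplan-Meier curves and summaries as description. The Table 4 entry and the shell would then agree.

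The cost is a paragraph of SAP text, one table block and short code, with no new data. The small downside is that the failure rule must be fixed in advance, and that the result is then a difference that counts failure as the worst outcome, which is not the quantity the censored curves describe.
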